6.3.3. PROTOCOL-SPECIFIC REPORTING INFORMATION

For the purpose of this protocol, mild (i.e., clinically non-significant) hypoglycemia and hyperglycemia symptoms or blood glucose values out of the normal range will not be reported as adverse events unless determined to meet the criteria of a Serious Adverse Event.

6.4. ANTICIPATED ADVERSE EFFECTS

The following adverse effects could occur in association with insertion, removal, and/or use of the Eversense CGM System Sensor and/or Transmitter:

- Infection, local or systemic, possibly resulting in Sensor removal
- Excessive bleeding during insertion or removal
- Bruising or swelling
- Poor incision healing after insertion or removal
- Keloid and/or scar formation
- Excessive or prolonged pain or discomfort at the Sensor site
- Nerve damage causing tingling, numbness, pain or weakness
- Uncomfortable heating
- Burn
- Electrostatic shock
- Skin irritation and/or redness
- Itch
- Discoloration of skin
- Skin thinning
- Hematoma formation
- Device migration
- Skin erosion
- Allergic reaction to the device components, local anesthetic, or other medication or materials used in the procedure

Senseonics, Inc.

Confidential Information

Page 32 of 43

Effective Date:#: 20 March

Protocol #: CTP-0034, Version 10

- Anxiety and/or nervousness and/or lack of sleep
- Device fragments or particulate matter remaining in the body
- Failure to retrieve device or device left behind
- Difficulty in removing device that may require surgery
- Device malfunctions of the Sensor and/or Transmitter with possible need to remove and/or replace the Sensor and/or Transmitter
- Burning sensation or pain.
- Elevated blood pressure
- Water retention in the tissue, swelling or edema
- Airway spasms
- Shortness of breath
- Circulatory disorders
- Confusion
- Disorientation
- Increased or decreased sensitivity to touch or pain
- Metallic taste
- Sleepiness
- Visual disturbances and/or blurred vision
- Tinnitus
- It is possible that the local anesthetic could cause a reaction other than listed or previously seen.
- Fluid/electrolyte disturbances such as fluid retention
- Muscle weakness
- Osteoporosis
- Peptic ulcer
- Pancreatitis
- Ulcerative esophagitis
- Impaired wound healing
- Headache

Senseonics, Inc.
Protocol #: CTP-0034, Version 10

Confidential Information

Page 33 of 43 Effective Date:#: 20 March

- Psychic disturbances and mood swings
- Convulsions
- Glaucoma
- Weight gain
- Nausea and/or vomiting
- Malaise
- Irritability
- Insomnia
- Heartburn
- Hyperglycemia
- Ketosis
- Headaches
- Dizziness, lightheadedness, and/or fainting
- It is possible that the use of the Eversense CGM system could cause a reaction other than listed or previously seen.
- It has not been determined whether the risks usually associated with injectable dexamethasone apply to the use of dexamethasone elution ring, a highly localized, controlled-release device.
- The dexamethasone ring could cause other adverse events not listed or previously seen.
- Other adverse events typically related to diabetes treatment and diabetes are unknown

6.5. INSERTION SITE ASSESSMENT

Assessments of the Sensor insertion and removal sites will take place by the clinician at each placement with physical exam and documentation of adverse events. The exam will include current and all previous Sensor sites as well as the surrounding area to capture any skin reactions resulting from attachment of the transmitter to the skin. These potential events include but are not limited to:

- Adhesive Patch Location Site Irritation including redness, excoriation or ulceration
- Sensor Location Site Pain/Discomfort
- Sensor Location Site Redness
- Sensor Location Site Infection

Senseonics, Inc.
Protocol #: CTP-0034, Version 10

Confidential Information

Page 34 of 43

Effective Date:#: 20 March

- Skin atrophy (thinning of the skin as compared to adjacent skin) over the Sensor
- Skin depigmentation (loss of coloration as compared to adjacent skin) over the Sensor
- Prolonged healing of incision site after insertion or removal (beyond expected 5-7days)

6.6. ESCALATION PLAN FOR SUSPECTED STEROID EXPOSURE

Patients will also be checked for complications that could possibly be related to systemic steroid exposure including;

- Poor wound healing
- Increased systemic infections
- Decreased bone density and risk of osteoporosis and/or fractures
- Suppression of the normal hypothalamic/pituitary axis
- Increased insulin resistance

Any subject demonstrating one or more of the conditions that could potentially be a result of steroid exposure listed above will undergo evaluation of the hypothalamic pituitary axis with standard 24-hour urine cortisol test and blood cortisol levels to rule out any systemic suppression as a result of steroid exposure.

6.7. RESIDUAL RISKS ASSOCIATED WITH THE DEVICE/ RMR-0019 US EVERSENSE E3 CGM SYSTEM RISK MANAGEMENT REPORT

Components of the Eversense CGM System are manufactured under the Quality System provisions of ISO 13485:2016 and 21 CFR 820.

Risk analysis has been performed and adequate control put in place as prescribed in relevant provisions of applicable regulatory requirements such as IEC 62304, ISO 14971, and IEC 60601-1, in accordance with the requirements of ISO 13485:2016. Residual risks associated with the device included risks in the categories of electromagnetic and thermal energy, biocompatibility, biologic, chemical and mechanical factors, and user-related error. All identified risks have been reduced as far as possible using various control methods including software revision and revalidation, hardware design modification, packaging and sterilization process validation and labeling revision. The calculated residual risks were determined to be acceptable for conduct of this clinical investigation.

6.8. DEVICE MALFUNCTIONS

All device deficiencies related to the identity, quality, durability, reliability, safety, or performance of a medical device shall be documented throughout the clinical investigation and appropriately managed by the Sponsor. Device deficiencies include malfunctions, use errors, and inadequate Senseonics, Inc.

Confidential Information

Page 35 of 43

Effective Date:#: 20 March

Protocol #: CTP-0034, Version 10

labeling.

Sensors that fail prior to the design life of 90 or 180 days will be returned to Senseonics for evaluation of the root cause of the premature Sensor failure. Summary results of such root cause evaluations will be presented in subsequent PAS reports.

6.9. RESIDUAL DXA TESTING

All Sensors removed after 12 and 24 (or 27 months as applicable) months participation (the subject's 4th and 8th Sensor for 90-day Sensor or 2nd and 4th for 180-day Sensor) will be returned after removal to Senseonics, where they will be assessed for residual DXA content in order to assess release rates of DXA in the broader intended use population.

7. DATA MANAGEMENT

All data will be prospectively collected by the HCPs and/or study coordinators and entered onto the electronic case report form (eCRF). All device data (calibration points, hours of wear time,) will be collected using the sponsor data management system (DMS). All data will be anonymous so that it will not be possible to identify a subject at any participating clinical center.

7.1. SOURCE DOCUMENTATION, CASE REPORT FORMS AND DATA MANAGEMENT

Data in this study will be collected on electronic Case Report Forms as well as retrieved from the web-based Data Management System (DMS).

Source Documents and Case Report Forms

The investigator or his/her designee at each site is responsible for recording investigation-related data onto the CRFs and maintain source documentation supporting the data. Good Clinical Practice in the documentation on source documents and CRFs will be followed. For source documentation or if papers CRFs are used, the data must be legibly written in ink. If changes are required, a single line is to be drawn through the incorrect information, the correct information written in and the change initialed and dated by the individual making the change. The reason for correction may be noted, unless obvious. Pencil, correction fluid or correction tape must not be used and incorrect information must not be obscured (scribbled-out).

The investigator must review, sign, and date the CRFs (electronically); these responsibilities cannot be delegated to another person. It is the investigator's responsibility to comply with regulatory requirements including, but not limited to, the maintenance of accurate, complete and current records relating to the CRFs.

The Sponsor (or their designee) will review the data against the original source documents and ensure any noted discrepancies are resolved by the study site, as described in the Monitoring

Senseonics, Inc.
Protocol #: CTP-0034, Version 10

Confidential Information

Page 36 of 43

- - -

Effective Date:#: 20 March

Plan. Subject data will be compared to information originally recorded on source documents related to the trial (i.e. professional notes, laboratory reports, investigation-specific worksheets, etc.).

Investigation-related information collected on eCRFs will be entered into a secure database. The database design and installation will be validated prior to use. Validation techniques used by Senseonics are consistent with applicable regulations and guidelines. Each database must pass a series of standard tests that demonstrate the usability and correctness of the database system to approved specifications. The test process generates detailed test result logs, which are provided as part of the database documentation.

The details of data review, database cleaning and data querying are described in a Data Quality and Management Plan (DQMP). This plan is updated throughout the investigation as amended data management requirements and investigation-specific data conventions are determined.

A comprehensive Electronic Data Capture (EDC) User Guideline will be developed for participating study sites describing general instructions on CRF completion; this guideline also includes investigation- specific data entry, and query management instructions.

Data entered by study sites will be reviewed by the Sponsor or their designee on an ongoing basis to ensure adequate query resolution and identify and query adverse events, protocol deviations, and any other ambiguous data points.

7.2. LABORATORY DATA

Results of laboratory tests (HbA1c) will be provided to the sponsor, with HbA1c results provided to clinical sites.

7.3. EVERSENSE CGM DATA FLOW PROCESS

Data from Subject Eversense CGM systems, including BG meter values that have been entered into the system as calibration values will be collected from the Eversense Data Management System (DMS). The Eversense Data Management System (DMS) is an accessory to compatible Eversense CGM products. It is a web-based application that may be used to view, analyze, and store glucose information from the Eversense CGM System. CGM data are wirelessly synchronized to the Eversense DMS by PAS subjects using the Share My Data feature on the Eversense mobile app.

8. STATISTICAL PLAN

The statistical plan is summarized below. Additional details concerning the analyses will be provided in the Statistical Analysis Plan (SAP) for the study.

Confidential Information

Senseonics, Inc.
Protocol #: CTP-0034, Version 10

n

Page 37 of 43 Effective Date:#: 20 March

8.1. ANALYSIS POPULATIONS

Primary Analysis population: The primary safety and effectiveness analyses will be based on data from all enrolled subjects in this post approval study (ITT, Intention-to-treat).

Per-Protocol Safety Analysis Population: A per-protocol (PP) population will be identified based on those subjects who met the original inclusion and exclusion criteria, have demonstrated substantial compliance with the protocol and no significant protocol deviations affecting the primary endpoints. Supportive analyses for the primary effectiveness endpoint and all secondary and exploratory analyses will be performed in the PP population.

8.2. PRIMARY ENDPOINTS

8.2.1. PRIMARY SAFETY ENDPOINT

The primary safety composite endpoint will be evaluated in the following hypothesis, against a Performance Goal of 4%:

H0: The rate of the composite of infection, secondary procedures to remove the Sensor, or procedure-related adverse events of at least moderate severity (p) is greater than or equal to 4%.

H1: The rate of the composite of infection, secondary procedures to remove the Sensor, or procedure-related adverse events of at least moderate severity (p) is less than 4%.

H1:
$$p < 4\%$$

The rate will be tested against the Performance Goal of 4%, using an exact, binomial test, with a one-sided p-value of 0.05 considered evidence of statistical significance. For the primary analysis, data will be analyzed on a per cycle basis, with each cycle contributing an independent observation.

As an additional analysis, analysis will be performed using a logistic regression model fit via generalized estimating equations and a working compound symmetric covariance structure; this allows for the modeling of potential within-subject correlation. The model will consist of only an intercept term; estimates will be transformed to the proportion scale to facilitate comparisons to the primary analysis of the performance goal.

An additional analysis will be performed based on only the first cycle for each subject. This will be based on an exact binomial method.

For each additional analysis, the estimate of the endpoint rate and the associated one-sided Senseonics, Inc.

Confidential Information

Page 38 of 43

Protocol #: CTP-0034, Version 10

Effective Date:#: 20 March

95% upper confidence bound will be calculated.

8.3. OTHER ENDPOINTS

Safety

Other safety endpoints will be summarized using descriptive statistics appropriate to the endpoint being evaluated. There are no formal hypotheses or tests for statistical significance associated with secondary endpoints.

The rates for serious and non-serious adverse events will be summarized as binomial proportions, together with the exact, one-sided upper 95% confidence bound. These will include insertion/removal procedure-related adverse events, and rate of device breakage.

Subgroup analysis of all safety endpoints based on:

- Age (<65 years vs. >65 years, minimum 40 subjects)
- Diabetes type (I vs. II)
- Race (non-Caucasian vs. Caucasian)

Effectiveness

Effectiveness will be measured as percentage change in the percent time in range (based on hours) at one month compared to 12 months using a time in range definition of glucose values between 70 mg/dL and 180 mg/dL. The Time in Range will be summarized as the mean of the subject percentages, together with the median, standard deviation, minimum, maximum, and 25th / 75th percentiles.

Summary statistics will also be provided for the change in HbA1c levels from baseline, and average hours of use per day.

Patient Perspective

Patient satisfaction as measured by validated questionnaires (CGM satisfaction survey and Diabetes Distress Scale) administered at select visits will be reported. The patient questionnaire scores will be summarized as means, median, standard deviation, minimum, maximum, and 25th / 75th percentiles.

Page 39 of 43

Effective Date:#: 20 March

Other Endpoints

Success rates for insertion and removal procedures will be presented to evaluate the

Senseonics, Inc. Confidential Information Protocol #: CTP-0034, Version 10

effectiveness of the training program. Success rate will also be presented based on the HCP experience with insertion and removing Sensors (learning curve by number of cases). It is anticipated that approximately 30% of the insertion and removal procedures will be done by nurse practitioners and physician assistants.

The rates of serious adverse events based on HCP experience with inserting and removing Sensors (learning curve by number of cases) will be examined.

8.4. SAMPLE SIZE JUSTIFICATION

8.4.1. PRIMARY SAFETY ENDPOINT:

A total of 1400 Sensor cycles contributing to the analysis is planned.

Based on data from the PRECISE (n=81 subjects), PRECISE II (n=90 subjects), PRECISION (n=35 subjects) and PMCF (n=1686 subjects) studies, a total of 31 events occurred that would meet the definition of the primary safety endpoint in this study. With a total of 1892 subjects, this equates to an observed rate of approximately 1.6% with an associated 95% confidence interval of 1.1% to 2.3%. As there is variability associated with this sample, as evidenced by the confidence interval, a conservative expected rate of events for this study is 2.3%. The planned sample size of 1400 total cycles) with this expected rate should provide greater than 95% power for the test of the performance goal of 4%.

Meeting the performance goal of 4% for the planned sample size would require a worst-case observation of a rate of approximately 3% or less (i.e., 41 or fewer events among 1400 cycles). This result will be clinically acceptable and similar to results observed in past studies.

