3.3. PRIMARY SAFETY HYPOTHESIS

The primary safety composite endpoint will be evaluated in the following hypothesis test against a Performance Goal of 4%:

H₀: The rate of the composite of infection, secondary procedures to remove the Sensor, or procedure-related adverse events of at least moderate severity (p) is greater than or equal to 4%.

$$H_0$$
: p ≥ 4%

H₁: The rate of the composite of infection, secondary procedures to remove the Sensor, or procedure-related adverse events of at least moderate severity (p) is less than 4%.

$$H_1$$
: p < 4%

The rate will be tested against the Performance Goal of 4%, using an exact, binomial test, with a one-sided p-value of 0.05 considered evidence of statistical significance. Data will be analyzed on a per cycle basis.

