3.1 Blinding

There is no blinding in this study.

Statistical Analysis Plan		Page 6 of 11
Sponsor	Study	Version
Senseonics	A Post Approval Study to Evaluate the Long-term Safety and Effectiveness of the Eversense® Continuous Glucose Monitoring (CGM) System	1.0

4 Sample Size Determination

At least 273 enrolled subjects will be inserted with Sensors to achieve at least 1400 Sensor cycles. Subjects will be encouraged to remain in the study up to 27 months of follow-up or after at least 1400 Sensor cycles are completed study wide.

Based on data from the PRECISE (n=81 subjects), PRECISE II (n=90 subjects), PRECISION (n=35 subjects) and PMCF (n=1686 subjects) studies, a total of 31 events occurred that would meet the definition of the primary safety endpoint in this study. With a total of 1892 subjects, this equates to an observed rate of approximately 1.6% with an associated 95% confidence interval of 1.1% to 2.3%. As there is variability associated with this sample, as evidenced by the confidence interval, a conservative expected rate of events for this study is 2.3%. The planned sample size of 1400 total cycles) with this expected rate should provide greater than 95% power for the test of the performance goal of 4%.

Meeting the performance goal of 4% for the planned sample size would require a worst-case observation of a rate of approximately 3% or less (i.e., 41 or fewer events among 1400 cycles). This result will be clinically acceptable and similar to results observed in past studies.

5 Statistical Analyses

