5.6.1.1 Primary Analysis

The primary safety composite endpoint will be evaluated in the following hypothesis, against a Performance Goal of 4%:

H0: The rate of the composite of infection, secondary procedures to remove the Sensor, or procedure-related adverse events of at least moderate severity (p) is greater than or equal to 4%.

$$H0: p \geq 4\%$$

H1: The rate of the composite of infection, secondary procedures to remove the Sensor, or procedure-related adverse events of at least moderate severity (p) is less than 4%.

$$H1: p < 4\%$$

The rate will be tested against the Performance Goal of 4%, using an exact, binomial test, with a one-sided p-value of 0.05 considered evidence of statistical significance. For the primary analysis, data will be analyzed on a per cycle basis, with each cycle contributing an independent observation.

The endpoint will be evaluated using the ITT analysis set.

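### The sample-size text sets the pass limit at 41 events in 1400 cycles, but the specified exact one-sided 0.05 test passes with up to 43

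*Protocol*

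**What the plan says.** The study has one formal hypothesis test: the composite safety rate per sensor cycle against a performance goal of 4%.

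- **Test and alpha.** Protocol 3.3: "The rate will be tested against the Performance Goal of 4%, using an exact, binomial test, with a one-sided p-value of 0.05". Protocol 8.2.1 repeats the level ("with a one-sided p-value of 0.05 considered evidence of statistical significance"), and so does SAP 5.6.1.1 ("using an exact, binomial test, with a one-sided p-value of 0.05 considered evidence of statistical significance"). Protocol 8.2.1 and SAP 5.6.1.1 treat each cycle as an independent observation.
- **Planning rate and power.** Protocol 8.4.1 plans 1400 cycles and takes 2.3% as the expected event rate. It says that this sample size "with this expected rate should provide greater than 95% power for the test of the performance goal of 4"%. SAP section 4 makes the same claim.
- **Pass limit.** Protocol 8.4.1 says that meeting the goal "would require a worst-case observation of a rate of approximately 3% or less (i.e., 41 or fewer events among 1400 cycles"). SAP section 4 gives the same count: "41 or fewer events among 1400 cycles".

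**The concern.** The largest passing count in an exact binomial test is an integer fixed by the number of cycles, the null rate and alpha. The documents give all three, so the count can be checked without any outside assumption, and 41 is not what they imply.

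The two statements part company at 42 or 43 events in 1400 cycles. There the specified test meets the goal, while the sample-size sections of both documents say that it is missed. A reader of the final report could then fairly ask whether the intended alpha was 0.05 or 0.025, and the documents would lend some support to either answer. That is better settled before the final count is known, particularly in an unblinded study with periodic interim summaries.

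**Working it through.** **Inputs**

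- n = 1400 cycles (Protocol 8.4.1, SAP section 4)
- p0 = 4%, exact binomial test, one-sided alpha 0.05 (Protocol 3.3 and 8.2.1, SAP 5.6.1.1)
- expected rate 2.3% (Protocol 8.4.1, SAP section 4)
- independent cycles, as the primary analysis states

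**Step 1. The planning rate reproduces.** 31/1892 = 1.64%, with a 95% Clopper-Pearson interval of 1.12% to 2.32%. This agrees with the printed 1.6% (1.1% to 2.3%), so the 2.3% is understood and is not in question.

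**Step 2. The pass limit.** The goal is met with k events if P(X ≤ k | n = 1400, p = 0.04) ≤ 0.05. Power is P(X ≤ k | n = 1400, p = 0.023).

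| Events k | k/1400 | Exact one-sided p | One-sided 95% upper bound | One-sided 97.5% upper bound | Power at 2.3% if k is the limit |
|---|---|---|---|---|---|
| 41 | 2.93% | 0.0203 | 3.78% | 3.95% | 94.7% |
| 42 | 3.00% | 0.0288 | 3.86% | 4.03% | 96.2% |
| 43 | 3.07% | 0.0400 | 3.94% | 4.12% | 97.4% |
| 44 | 3.14% | 0.0545 | 4.02% | 4.20% | 98.2% |

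At one-sided 0.05 the limit is 43. At one-sided 0.025 it is 41, because 41 gives 0.0203 and 42 gives 0.0288.

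**Step 3. Does another method give 41 at one-sided 0.05?** No. The score test, with or without continuity correction, and the Poisson approximation give 43. The mid-p version gives 44 and the Wald bound gives 45.

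**Step 4. Does another number of cycles give 41?** Under the exact test at one-sided 0.05, 41 is the limit only for 1324 to 1351 cycles, below the planned 1400. The limit is 43 for 1380 to 1407 cycles and 44 for 1408 to 1435.

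**Step 5. The power claim.** A limit of 41 gives 94.7% at 2.3%, just under the stated figure of more than 95%. A limit of 43 gives 97.4%, which satisfies it.

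**Step 6. How often it would matter.** P(X = 42 or 43) = 0.9739 − 0.9469 = 0.0270 at a 2.3% rate. At the observed 1.64% it is about 0.00015.

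**The case against.** The strongest reply is that nothing operative depends on the count. The decision rule in Protocol 8.2.1 and SAP 5.6.1.1 is a p-value, and 41 appears only in the justification of the sample size. It errs on the strict side, so it cannot create a false claim of success. The plan is for at least 1400 cycles, so any printed count is illustrative, and the rounded figure of about 3% fits both 2.93% and 3.07%. The SAP paragraph repeats the protocol's, so this is one slip carried over, not two. All of this stands and keeps the point minor, but it does not make 41 correct for the stated test.

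A second reply is that the power argument is thin. The gap is 0.3 percentage points, it closes if the true planning rate is slightly lower (a limit of 41 gives 96.0% at 2.25%), and a limit of 42 would also satisfy the claim (96.2%). That is fair. The unrounded upper confidence limit of 2.32% moves the other way (94.2% with 41), but power is supporting evidence only. The p-values establish the mismatch by themselves.

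A third reply is that the documents cannot prove whether the count or the alpha was the slip. That also stands. Three statements of one-sided 0.05, together with the power claim, point to the count, but the sponsor has to confirm it.

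**Conclusion.** The concern holds. For 1400 cycles, a 4% null rate and the stated exact one-sided 0.05 test, the limit is 43 events (3.07%), not 41 (2.93%). The figure of 41 belongs to a one-sided 0.025 test that neither document specifies. The stated alpha and the stated power agree with 43, and 41 fits neither.

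Severity is minor: the error is conservative, the test in SAP 5.6.1.1 governs, and the formal result does not change. The limit itself needs no assumption beyond the independence of cycles, which the primary analysis adopts. The power figures also take 2.3% as the true rate.

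**What to change.** In Protocol 8.4.1 and SAP section 4, replace the count of 41 with 43 (3.07%), label it as the limit for exactly 1400 cycles, and say that it will be recalculated for the final number of cycles. Alpha and the power statement stay as they are. The sentence that follows in both documents calls the worst-case result clinically acceptable and in line with past studies, so the sponsor should confirm that this judgement still holds at 3.07%.

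If the sponsor meant one-sided 0.025, keep 41, restate the alpha in Protocol 3.3 and 8.2.1 and SAP 5.6.1.1, and correct the power to 94.7% in Protocol 8.4.1 and SAP section 4.

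The first route costs one number and a short label in each document, with no change to the test, the sample size, participants or procedures. The second changes the stated test level and so needs more edits, but it also leaves sample size and procedures alone.
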